Outcomes	Function						
	Barthel Index (primary outcome)	X		X	X	X	X
	Gait speed	X		X	X		
	6-minute walk	X			X		
	Depression SCID (given if indicated by MADRS)	X					
	MADRS	X		X			
	17-item positive and negative affect scale	X	X	X		X	X
Processes	Rehabilitation intensity						
	Patient active time & actigraphy (at 20% of sessions at random)	collected each session throughout stay					
	Treatment engagement						
	Observer-rated Rehabilitation Participation Scale (at 20% of sessions at random)	collected each session throughout stay					
	Fidelity data (at 20% of session at random)	collected each session throughout stay					
	Post-Treatment Affect						
	Self-Assessment Moniker (at 20% of session at random)	collected each session throughout stay					
	Patient Satisfaction and Treatment Fidelity Survey	Collected after therapy sessions throughout stay					
	Other rehabilitation variables						
	Rehospitalization			X	X	X	X

Disposition (home, long-term care)	X		X	X	X	X
Social Participation (PROMIS Ability to Participate in Social Roles and Activities)					X	X
Instrumental Activities of Daily Living (OARS IADL)					X	X
Executive Functioning (Clock Drawing Test)	X					
Fear of Falling	X					
Readiness for Rehab	X	X				
Short Blessed Test	X					
Medical Comorbidity (CIRS-G)	X					
Barthel Index: Pre-morbid version	X					

F3 SNF Admit (Baseline) Visit

The baseline visit will take place immediately or soon after the patient consents to the study. The rater will conduct the following assessments: Barthel, 6 minute walk, gait speed, SCID, MADRS, PANAS, Disposition, Clock Drawing Test, Fear of Falling, Readiness for Rehab, CIRS-G, Barthel Index: Pre-morbid version.

F4 Day 7 Visit

The day 7 visit will take place 7 days after the patient consents to the study. The rater will conduct the following assessments: PANAS, Readiness for Rehab.

F5 Day 30 Visit

The day 30 visit will take place 30 days after the patient's date of admission to the facility. If the patient has already been discharged from the skilled nursing facility, the rater will call the patient to schedule a home visit to conduct the following assessments: Barthel, gait speed, MADRS, PANAS, Follow-up Disposition.

F6 SNF Discharge

The discharge visit will take place as close in time to the patient's discharge date as possible. The rater will conduct the following assessments at the skilled nursing facility: Barthel, 6 minute walk, gait speed, Discharge Location..

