Time course analyses will be conducted to investigate the differences between pre and post outcome measures. These analyses will be used to ascertain whether there is a statistically significant difference in change over time between the EMR group and the SOC group, controlling for baseline values. Analyses of the outcome measures for normality will be carried out. Time course analysis techniques such as mixed effects models, t test of the differences, Wilcoxon test of the differences, or ANCOVA on the differences (using baseline value as the covariate) will then be conducted, depending on the normality tests. Our favored method for the primary analysis of baseline to day 30 (i.e., pre-post treatment) effects is the ANCOVA approach, comparing the EMR and standard-of-care groups in change scores, covarying for baseline scores. This approach is recommended as the superior and most well-powered approach for examining pre-post RCT data.⁹¹ Our tests of the pilot data agreed with this: the ANCOVA approach had as much or more statistical power than other approaches (t-test, Wilcoxon, mixed-effect model) for all outcomes.

Participants will be randomized within each facility (i.e., stratified by facility) and then receive a PT/OT therapist pair who either is or is not trained/supervised in EMR based on randomization assignment. Thus participants are nested within therapists and therapists are nested within facilities. This multi-stage nested (hierarchical) design structure introduces possible correlation of participant outcomes with therapist. Such classification effects (facility/therapist) will be analyzed using Proc Nested in SAS or with the multi-level modeling available in Mplus that deals with stratification, clustering, and weighting.

We will also examine all time points to Day 90, to provide a real-world estimate of EMR and improve power to detect important secondary outcomes such as rehospitalization and institutionalization. We acknowledge these data may become somewhat naturalistic

in a rehabilitation population, given differences in length of stay, transfers to different facilities, and re-hospitalizations. Mixed effects models are the preferred method for these multiple-time-point analyses, especially as some missing data are to be expected post-discharge.⁹²

H Data Handling and Record Keeping

H1 Confidentiality and Security

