The primary measure employed for assessing functional improvement will be The Barthel Index. This index is a 10-item scale used to ascertain the degree of independence of normal daily activities. This will be done by taking the sum of these 10 items. A high score indicates a high degree of independence, and a score can range from 0 to 100.

- 2) Aim 2: Examine EMR's ability to overcome patient-level barriers to successful rehabilitation.

H2: The effectiveness of EMR for functional recovery will be greatest in: (a) patients with clinical depression; (b) patients with high levels of medical comorbidity; (c) patients with cognitive impairment.

Part (a) will be assessed using the MADRS, which is a 10-item scale used to assess for major depression. Each item is rated on a scale of 0 to 6, where a 6 is worse. The total score (i.e., sum of these 10 items) will be

used to assess for major depression and can range from 0 to 60.

Part (b) will be assessed using the CIRS-G, which is a 13-item scale used to assess for disease in all major body systems. Each item is rated on a scale of 0 to 4, with a 4 indicating severe impairment. The total score (i.e., sum of these 10 items) will be used to assess for medical comorbidity and can range from 0 to 52.

Part (c) will be assessed using the SBT Scores. The SBT is a 6-item scale used to assess for memory/concentration deficits. A total score, which is obtained after applying a weighting factor to each item then summing up the final item scores, can range from 0 to 28. A high score indicates impairment consistent with dementia.

ii. Analysis Methods

The primary outcome analysis for functional recovery will use a marginal model with time (baseline and discharge), condition (E-MR vs. SOC) and time x condition as fixed effects and with a covariance structure specified based on the Bayesian Information Criterion (BIC). Employing a marginal model allows for a more robust approach in the handling of missing data compared to the traditional ANCOVA model.

For H2 under Aim 2, each potential continuous moderator will be individually inserted into the primary model. The term of interest will be the time x condition x moderator interaction.

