The secondary analyses for Six-Minute Walk distance and Gait Speed will use a Mann-Whitney U Test to test for differences in means between groups. In addition, a Chi-Square test will be employed to test for independence between condition and the secondary outcome variable re-hospitalization. Finally, the outcome of self-reported function will use a marginal model using time (30, 60, and 90 days), condition and time x condition as fixed effects, with a covariance structure specified based on BIC.

Exploratory analyses will also test whether the effects of age, gender, race and site (i.e., Barnes Jewish Extended Care Vs Alexian Brothers Sherbrooke Village) altered the conclusions of the primary results as well as the conclusions of the moderator results.

Note: we will not look at the nesting of subjects within therapists who are then nested within site as this is not possible due to the inconsistency of assigning therapists to participants.

iii. Missing Data

We use a marginal model which accounts for missing data (no multiple imputation was used).

iv. Harms

An adverse event (AE) is any untoward medical occurrence in a subject temporally associated with participation in the clinical study or with use of the experimental agent being studied. An adverse finding can include a sign, symptom, abnormal assessment (laboratory test value, vital signs, electrocardiogram finding, etc.), or any combination of these.

AEs will be labeled according to severity (i.e., mild, moderate or severe), which is based on the AE's impact on the participant.

AEs will be categorized according to the likelihood that they are related to the study intervention or other study procedures (i.e., definitely unrelated, definitely related, probably related, or possibly related).

SAEs that are unanticipated, serious, and possibly related to the study intervention will be reported to the IRB, and NIMH in accordance with requirements. Unexpected fatal or life-threatening AEs related to the intervention will be reported to the NIMH Program Officer within 7 days. Other serious and unexpected AEs related to the intervention will be reported to the NIMH Program Official within 15 days. Anticipated SAEs will be handled in a less urgent manner but will be reported to the IRB in accordance with their requirements.

v. Statistical Software

All analyses will be performed using SAS and/or R.

vi. References

none

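### The SAP's two-occasion marginal model handles missing discharge Barthel scores no more robustly than ANCOVA, and is less precise

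*SAP*

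**What the plan says.** - SAP, Analysis ii (Analysis Methods): the primary Barthel analysis is a "marginal model with time (baseline and discharge), condition (E-MR vs. SOC) and time x condition as fixed effects", with the covariance structure chosen by BIC. The reason for preferring it follows at once: "Employing a marginal model allows for a more robust approach in the handling of missing data compared to the traditional ANCOVA model".
- SAP, Analysis iii (Missing Data), in full: "We use a marginal model which accounts for missing data (no multiple imputation was used". No missingness assumption and no sensitivity analysis for missing data is stated.
- Protocol G4: the favoured primary analysis is "the ANCOVA approach, comparing the EMR and standard-of-care groups in change scores, covarying for baseline scores". The protocol there calls it the best-powered option for pre-post data. The SAP's sample size paragraph still refers to an ANCOVA difference.
- Both assessment schedules place the Barthel at baseline, Day 30, discharge, Day 60 and Day 90. For Day 30, Protocol F5 says: "If the patient has already been discharged from the skilled nursing facility, the rater will call the patient to schedule a home visit".
- In the SAP, function at 30, 60 and 90 days has its own secondary model and does not enter the primary one.
- Participants who withdraw are not followed, apart from an attempt to obtain prognosis information (Protocol E2, 2.g; SAP, Withdrawal/follow-up).

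**The concern.** A likelihood model improves on a complete-case analysis when it holds some post-baseline information on people whose primary score is missing. The SAP's primary model holds none: someone without a discharge score contributes a baseline value only. Yet the claimed gain is the sole reason given for leaving ANCOVA, and the model is the whole missing-data strategy.

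Two things are at stake. A reader of the results would credit the analysis with a protection that it lacks. And the change of model gives up precision that ANCOVA would have kept.

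**Working it through.** **1. The plan's own figure.** The robustness claim rests on no number. The nearest stated figure is N=252 (Protocol, opening summary), with d=0.4, 80% power and two-sided alpha 0.025. The normal approximation gives 2(2.241+0.842)²/0.4² ≈ 119 per arm, 238 in total; the t-based figure is 242. Power at 252 is about 82%. The difference from 252 is on the safe side and does not bear on this point.

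**2. The estimate.** Choosing a covariance by BIC implies a likelihood fit. Take an unstructured covariance common to both arms, with only discharge scores missing. Maximum likelihood then sets each arm's discharge mean to

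(observed discharge mean) + b × (baseline mean of all randomized − baseline mean of those with a discharge score),

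where b is the pooled within-arm slope of discharge on baseline in those with both scores. This is the ANCOVA slope; putting change on the left-hand side, as the protocol does, leaves the treatment coefficient unchanged. Take the EMR–SOC difference, then subtract the baseline difference in all randomized, D:

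time × condition = complete-case ANCOVA effect − (1 − b) × D.

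In simulated data the identity held to within 2e-10 in every dataset. Baseline-only participants enter solely through D, which is chance imbalance. Both analyses are therefore valid under the same condition: missingness depends only on baseline and arm.

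The other structures BIC could choose at two occasions only add restrictions. Independence would make the estimate rest on raw observed means, which is less robust than ANCOVA.

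**3. Precision, complete data.** In units of the outcome variance, time × condition has variance proportional to 2(1−r) and ANCOVA to 1−r². The ratio is 2/(1+r). The correlation r is an assumption, and d is taken in outcome-SD units.

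| r | Variance ratio | Power, SAP term | Power, ANCOVA |
|---|---|---|---|
| 0.3 | 1.54 | 67% | 86% |
| 0.5 | 1.33 | 82% | 92% |
| 0.7 | 1.18 | 97% | 99% |

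(N=252, d=0.4, two-sided alpha 0.025.) At r=0.5 the SEs are √(4/252) = 0.126 SD and √(0.75×4/252) = 0.109 SD. At the 5% level stated in the SAP's Statistical Principles, power at r=0.5 is 89% against 96%.

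**4. Bias when missingness follows later function.** Assumed: SD 20, true effect 8 points (d=0.4), baseline–discharge correlation 0.5, discharge–Day 30 correlation 0.7, 15% of discharge scores missing, 400 simulated trials per row. Simulation error of a mean is about 2.7/√400 ≈ 0.13 points. Entries are bias (SE) in points.

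| Missingness driven by | Day 30 seen, if discharge missing | ANCOVA | SAP model | SAP model + Day 30 | Common baseline + Day 30 |
|---|---|---|---|---|---|
| Baseline and arm | half | −0.11 (2.36) | −0.05 (2.68) | −0.02 (2.67) | −0.08 (2.33) |
| Day 30, SOC only | all | −2.10 (2.39) | −2.07 (2.69) | −0.06 (2.61) | −0.09 (2.30) |
| Day 30, SOC only | half | −2.20 (2.32) | −2.34 (2.68) | −1.25 (2.69) | −1.11 (2.32) |
| Baseline and arm | none | −0.07 (2.45) | −0.06 (2.68) | −0.06 (2.68) | −0.07 (2.45) |

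The SAP model tracks ANCOVA in bias and has the larger SE. In the last row, adding Day 30 changes nothing.

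**5. Milder mechanism.** Here missingness depends on Day 30 function in both arms, with discharge–Day 30 correlation 0.8 and 10–30% missing in SOC. The two-occasion bias runs from −3% to −16% of d=0.4, that is 0.012 to 0.064 SD. In one such case (16% SOC and 10% EMR missing, true effect 0.40) the two-occasion estimate was about 0.355. Adding Day 30 gave 0.396, 0.380 or 0.359 when all, half or none of those missing discharge had a Day 30 score. With half, the share of the shortfall recovered is (0.380−0.355)/(0.40−0.355) = 56%, or 61% of the gain reached when all have Day 30 (0.025/0.041). In step 4 it was 47–50%.

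**The case against.** The algebra is hard to dispute; the fair objections concern scope.

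- **A reader might infer that adding Day 30 repairs the missing data.** The documents do not support that. Withdrawn participants are not followed and would usually lack both scores. The overlap is not stated, so full recovery is the best case. If missingness depends on the discharge score itself, Day 30 only roughly halves the bias even when it is always observed.
- **A reader might infer that discharge scores will be missing more in those who do badly, so the EMR effect is understated.** Plausible, but not in the documents. Protocol G4 says "Mixed effects models are the preferred method for these multiple-time-point analyses, especially as some missing data are to be expected post-discharge". That concerns analyses out to Day 90, and transfers and re-hospitalizations are mentioned there to describe those later data. Discharge is assessed in the facility, near the discharge date. No missing rate is given, and arm-specific missingness could move the bias either way.
- **The marginal model does have some advantages.** It uses a participant with a discharge score but no baseline, which should be rare because baseline follows consent closely. It also beats a complete-case comparison of raw change (bias about 1.7 points under baseline-driven missingness in step 4). But the SAP's stated comparator is ANCOVA.
- **Visits may not be comparable.** Day 60 may be done by phone. With stays of about three weeks, Day 30 usually but not always follows discharge. The SAP calls its 30/60/90-day outcome self-reported function without saying that it is the Barthel.
- **Timing.** The SAP already reports the number of depression diagnoses and is partly in the past tense, so changing the primary model is more than an edit of wording.

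All of these limit the size of the gain and the choice of remedy. None restores the claimed advantage over ANCOVA.

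**Conclusion.** The robustness statement is wrong as written and should go. That rests on algebra for the unstructured two-occasion model with only discharge scores missing, and needs no assumed rate. The loss of precision against ANCOVA is equally firm in form; its size (variance ratio 1.33, power 82% against 92%) depends on the assumed correlation of 0.5.

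The bias figures are illustrations. Roughly 3–16% of d=0.4 follows from assumed missingness of 10–30% driven by Day 30 function. The one-armed mechanism in step 4 gives 2.07/8 to 2.34/8, or 26–29%. For scale, the complete-data SE of the SAP term at r=0.5 is 0.126 SD, about twice the largest bias of the milder mechanism (0.064 SD).

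It would go too far to call the planned analysis invalid or its result biased. It is as valid as complete-case ANCOVA, under the same assumption.

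**What to change.** 1. In SAP Analysis ii, delete the sentence that claims greater robustness than ANCOVA.
2. In SAP Analysis iii, state that the model assumes data missing at random given the observed Barthel scores.
3. Fit the primary Barthel model with baseline, Day 30 and discharge (optionally Days 60 and 90) as responses, visit by condition, an unstructured covariance and a baseline mean common to both arms, or with baseline as a covariate. Keep the EMR–SOC contrast at the declared primary visit. The common baseline matters: adding Day 30 while leaving baseline means free by arm would keep the loss of precision.
4. If the sponsor does not want a multi-visit primary model, restore ANCOVA at the declared primary visit and run the multi-visit model as a sensitivity analysis.
5. Report how many participants missing discharge have a Day 30 score, since the benefit depends on it.

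Cost: no new visits or data. There are a few more covariance parameters, and visits must be treated as labels because Day 30 falls before discharge for some and after for others. Day 60 may differ in mode if taken by phone, so Day 30 is the main addition. Because the SAP already contains trial data, the change should be dated and justified there.

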Therefore, we created Enhanced Medical Rehabilitation (EMR) for older adults. A real-world adaptation of the science of behavior change, EMR is an integrated set of skills for physical and occupational therapists (PT/OT) that transform standard post-acute rehabilitation through: (1) a patient-directed, interactive approach (2) increased rehabilitation intensity (3) frequent feedback to patients on effort and progress. We developed training and supervision techniques so that PT/OTs carry out these skills with high treatment integrity.

In NIMH R34 pilot work, we found: (1) EMR is high-intensity and engaging: therapy by PT/OTs trained and supervised in EMR is greatly amplified in intensity and patient engagement compared to standard-of-care rehabilitation. (2) EMR improves functional and affective recovery: patients randomized to EMR had better improvement of function, physical performance, and positive and negative affect. (3) EMR overcomes barriers to rehabilitation: patients with depressive symptoms, cognitive impairment, and multiple medical comorbidities benefitted most from EMR relative to standard therapy.

We propose a randomized trial that will test EMR's benefits over standard-of-care rehabilitation for affective and functional recovery. Our aims are (1) examine the effectiveness of EMR for improving functional and affective outcomes in 252 older adults admitted to SNFs for post-acute rehabilitation, and (2) examine EMR's ability to overcome patient-level barriers (such as depression) to successful rehabilitation.

The innovation of this project is high: it is a novel application of theories of behavior change to improve both affect and function. It responds to NIMH strategic plan objective 3, "Develop new and better interventions for mental disorders that incorporate the diverse needs and circumstances of people with mental illness."

The public health significance is also high: recovery from disablement is a health issue of enormous human and economic significance. Success in this line of research will make rehabilitation more effective. Doing so would benefit all older adults in this sector of care but particularly those with depression, cognitive impairment, and other complications. This project addresses NIMH's goal of interventions to improve mental health and related health outcomes in real-world settings.

A2 Study Aims and Hypotheses

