2. PROMIS (Ability to Participate in Social Roles and Activities).
3. OARS IADL.

Process data: Measures of the dosage of intervention (# of EMR steps done in each therapy activity; PAT %; Rehab Participation Scale Score) before and after training.

Study Methods:

i. Trial Design:

This was a randomized, parallel-group trial where patients received either EMR or SOC therapy.

Patients who received EMR received therapy only from therapists who were trained and supervised in EMR. Their therapy sessions followed the EMR protocol. Otherwise, their SNF care did not differ from usual care.

Patients who received SOC received therapy only from PT/OTs (or assistants) who were not trained nor supervised in EMR. These therapists were monitored (videotaped or observed) but were not asked to do anything differently with their patients.

ii. Randomization:

Randomization (blocks...2 and 4 patients). was 1:1 to EMR or SOC with stratification by SNF site and by baseline depression status.

iii. Sample Size:

The sample size was based on 80% power to detect a Cohen's $d=0.4$ effect size on the ANCOVA difference in treatments at primary endpoint, based on a two-tailed $p<0.025$ (because two outcome measures are used). G*Power 3.1.2 was used for power calculations. A Cohen's $d=0.4$ is between "small" (0.2) and "medium" (0.5) effect sizes. Effect sizes for function were in the "large" range, $d=0.7-0.9$, but we acknowledge that these observed effect sizes are qualified by the small sample size, and it makes most sense to be more cautious regarding likely effect sizes in a full-scale study, hence our choice to power at $d=0.4$. Such an effect size is clinically relevant for the functional outcomes. *We will only examine affective recovery as an outcome for those who are "affectively impaired" to begin with; i.e., those with clinical depression at baseline; with this reduced N, we are powered at 80% for a $d=0.54$. This same power analysis would apply for any subgroup analysis of depressed; i.e., if we wish to demonstrate that EMR is effective both in the case of clinical depression and in "non-depressed" older adults.*

iv. Statistical Interim Analyses/Stopping Guidance:

Not applicable; we did not have any interim data analysis or early stopping plans.

v. Timing of Final Analysis:

All outcomes will be analyzed collectively.

vi. Timing of Outcome Assessments (including windows):

	Schedule of Assessments	SNF admit (baseline)	Day 7	Day 30	SNF discharg e	Day 60	Day 90

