Outcomes	Function						
	Barthel Index (primary outcome)	X		X	X	X	X
	Gait speed	X		X	X		
	6-minute walk	X			X		
	Depression SCID (given if indicated by MADRS)	X					
	MADRS	X		X			
	17-item positive and negative affect scale	X	X	X		X	X

Processes	Rehabilitation intensity					
	Patient active time & actigraphy (at 20% of sessions at random)	collected each session throughout stay				
	Treatment engagement					
	Observer-rated Rehabilitation Participation Scale (at 20% of sessions at random)	collected each session throughout stay				
	Fidelity data (at 20% of session at random)	collected each session throughout stay				
	Post-Treatment Affect					
	Self-Assessment Moniker (at 20% of session at random)	collected each session throughout stay				
	Patient Satisfaction and Treatment Fidelity Survey	Collected after therapy sessions				
	Other rehabilitation variables					
	Rehospitalization		X	X	X	X
	Disposition (home, long-term care)	X	X	X	X	X
	Social Participation (PROMIS Ability to Participate in Social Roles and Activities)				X	X
	Instrumental Activities of Daily Living (OARS IADL)				X	X
	Executive Functioning (Clock Drawing Test)	X				
	Fear of Falling	X				
	Readiness for Rehab	X	X			
	Short Blessed Test	X				
	Medical Comorbidity (CIRS-G)	X				
	Barthel Index: Pre-morbid version	X				

Statistical Principles:

i. Confidence Intervals and P-Values

Level of significance is 5%

ii. Adherence and protocol deviations

Protocol Deviation:

Any alteration or modification to the IRB-approved research without prospective IRB approval. The term research encompasses all IRB-approved materials and documents including the detailed protocol, IRB application, consent form, recruitment materials, questionnaires/data collection forms, and any other information relating to the research study.

Therapist adherence and competence was tracked two times per participant.

Variables: number of EMR principles used per therapy session; PAT.

iii. Analysis Populations

Trial Population:

- i. Screening data to describe representativeness of trial sample will include age, gender, race and ethnicity.
- ii. Eligibility

Inclusion Criteria:

- a. 65 years of age and older
- b. Admitted to a skilled nursing facility for post-acute care from PT and OT for 2 weeks or more.

Exclusion Criteria:

- a. Language, visual or hearing barriers to participation (e.g. unable to communicate with research staff).

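### The SAP calls the Mann-Whitney test of the walking outcomes a test of means, does not say what quantity is compared, and leaves baseline out of the Day 30/60/90 function model; the cost is precision, not bias

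*SAP*

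**What the plan says.** The SAP, Analysis, ii. Analysis Methods, covers six-minute walk distance and gait speed in one sentence: they "will use a Mann-Whitney U Test to test for differences in means between groups". Nothing there says which visit is analysed, whether the follow-up value or the change is compared, or what estimate will accompany the p-value.

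The SAP's Additional Variables/Outcomes section and its assessment schedule show both measures at baseline and discharge, with gait speed also at Day 30. Patients unable to do the six-minute walk are entered as 0 feet. For gait speed, they are entered as 0 meters and 0 seconds.

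Self-reported function gets a "marginal model using time (30, 60, and 90 days), condition and time x condition as fixed effects". The instrument is not named. In the schedule, the Barthel Index is the only function scale due at Days 30, 60 and 90, so it is the likely one, and it has a baseline.

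Protocol G4 plans to compare change between groups "controlling for baseline values". The SAP's own primary model keeps baseline, as a time point. Site is a stratification factor, but the SAP's exploratory check on site covers only the primary and moderator results.

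**The concern.** There are three separate problems.

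1. The hypothesis is misdescribed. Mann-Whitney asks whether values in one arm tend to exceed those in the other. It is a test of location shift only if the two distributions have the same shape. With a cluster of zeros for patients who cannot walk, the shapes may well differ between arms.
2. The walking analysis is not pinned down. Gait speed has two follow-up visits, and each measure could be analysed as a value or as a change. These choices give different p-values, and the SAP leaves them open.
3. A baseline that has already been collected is left out of the function model, and no baseline term is named for the walking tests. Variance that baseline could explain then stays in the error term, and chance imbalance adds noise to the estimates.

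These outcomes would be read as support for, or against, the primary Barthel result. An imprecise comparison whose contrast is unclear weakens that reading.

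**Working it through.** **The plan's own figure.** The documents give no power, SD or effect size for the walking outcomes or for Day 30/60/90 function. The only sizing is for the primary analysis: the protocol introduction plans the trial "in 252 older adults admitted to SNFs for post-acute rehabilitation", and the SAP claims "80% power to detect a Cohen's $d=0.4$ effect size on the ANCOVA difference in treatments at primary endpoint", at two-sided 0.025. Per arm, n = 2(2.241 + 0.842)²/0.4² = 118.8, so 119, or 238 in total (242 with the t distribution). With 252, power is about 82%. That is a small surplus and has no bearing on this point.

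**Is Mann-Whitney a test of means?** In 4,000 simulated trials of 126 per arm, one arm was lognormal (log-mean 0, log-SD 1) and the other normal with SD 0.3 and the same mean, exp(0.5). Mann-Whitney rejected in 99.7% of trials and the Welch t test in 7.5%. The shapes are deliberately extreme. The example shows that the two hypotheses differ, not how far apart they would be in this trial.

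**Power by large-sample formula.** Inputs from the documents are 252/2 = 126 per arm and the 5% level in the SAP's Statistical Principles. Assumptions are a two-sided test, complete data, normal outcomes, an effect of d = 0.4 follow-up SD (borrowed from the primary sizing) and a baseline-to-follow-up correlation r of 0.3, 0.5 or 0.7.

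Power = Φ(d·√(n/2)/s − 1.96), with d·√(n/2) = 0.4 × √63 = 3.175. The effective SD s is:

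- Mann-Whitney on the follow-up value: 1/√(3/π) = 1.023. Power is Φ(3.10 − 1.96) = 87.3% at any r.
- Mann-Whitney on change: √(2(1 − r)) × 1.023. Power is 74.6%, 87.3% and 98.0%.
- ANCOVA: √(1 − r²). Power is 91.4%, 95.6% and 99.4%.

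**Power by simulation.** These runs add rank ANCOVA, in which ranked follow-up is regressed on arm and ranked baseline. In the rows with zeros, 30% of baselines and about 15% of control follow-up values are 0 and the rest are right-skewed; d and r then apply to the underlying normal scale. The 120-per-arm, 0.3 SD setting is purely an assumption. It used 3,000 trials per cell and the others 4,000, so sampling error is about 1 point or less.

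| Setting | r | Mann-Whitney, follow-up | Mann-Whitney, change | Rank ANCOVA | Gain over follow-up | Gain over change |
|---|---|---|---|---|---|---|
| 126/arm, 0.4 SD, normal | 0.3 | 87.2% | 74.3% | 89.5% | 2.3 | 15.2 |
| | 0.5 | 87.4% | 87.1% | 94.0% | 6.6 | 6.9 |
| | 0.7 | 87.0% | 97.8% | 99.0% | 12.0 | 1.2 |
| 126/arm, 0.4 SD, skewed with zeros | 0.3 | 86.6% | 68.4% | 89.0% | 2.4 | 20.6 |
| | 0.5 | 86.6% | 82.0% | 93.2% | 6.6 | 11.2 |
| | 0.7 | 86.9% | 95.2% | 98.2% | 11.3 | 3.0 |
| 120/arm, 0.3 SD, normal | 0.3 | 63% | 50% | 67% | 4 | 17 |
| | 0.5 | 61% | 63% | 73% | 12 | 10 |
| | 0.7 | 61% | 82% | 86% | 25 | 4 |

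A repeat of the 120-per-arm, r = 0.3 cell gave a gain over change of 18 points, within simulation error of 17. Rank ANCOVA was ahead of both Mann-Whitney versions in every cell. Ordinary ANCOVA on the skewed data was no better than Mann-Whitney on follow-up at r = 0.3 (86.6% for both) and 5 points better at r = 0.5 (91.6% against 86.6%). The rank form is therefore the safer way to adjust.

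**Day 30/60/90 function.** If baseline has the same correlation r with each visit, adding it reduces residual variance by r²: 9%, 25% and 49% at r = 0.3, 0.5 and 0.7. The standard error is multiplied by √(1 − r²) = 0.95, 0.87 and 0.71.

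**The case against.** The strongest reply is that the SAP may intend the walking test to be run on change scores. Protocol G4 lists a Wilcoxon test on the differences among its options, with the choice depending on normality, and names ANCOVA as the favoured method for the primary analysis only. Protocol G3 allows nonparametric alternatives. A rank method is also sensible when patients unable to walk are scored 0.

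Much of this stands. A reader might infer that the SAP discards the walking baselines. The text does not establish that, because it is silent on value versus change. What can be said is that the analysed quantity is unspecified. The defence of rank methods also stands, and the fix keeps one. It does not remove the precision point, since Mann-Whitney on change was also below rank ANCOVA at every correlation tried. Nor does the SAP's reason for leaving ANCOVA in the primary analysis, the handling of missing data, carry over: Mann-Whitney simply drops patients with missing values.

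A reader might also infer biased results or an inflated type I error. Neither follows, because allocation is randomised and chance imbalance is already reflected in the test's error rate. Nor do the documents show that a significant result would be reported as a mean difference, since no estimate is specified.

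**Conclusion.** The point holds in a limited form. Describing Mann-Whitney as a test of means is wrong on the face of the text. The missing time point, analysed quantity, baseline term and effect estimate for the walking outcomes are also plain from the text, as is the absence of baseline from the Day 30/60/90 model. That the function instrument is the Barthel is an inference from the schedule.

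The size is conditional. Under the assumptions above, rank ANCOVA gains about 2 to 25 power points over Mann-Whitney on the follow-up value, most at high correlation. Over Mann-Whitney on change it gains about 1 to 18 points with normal data, and up to about 21 in the runs with zeros, least at high correlation. No single figure can be asserted, because the documents give no correlation, SD or effect for these outcomes.

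Two further steps are tempting but unsupported. Choosing the covariance structure by BIC is not shown to be an error. A depression-stratum covariate is hard to justify when the SAP reports only 14 participants with a diagnosis. The primary analysis is unaffected. This is a change worth making to the secondary analyses, at little cost.

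**What to change.** - **Six-minute walk and gait speed.** Name discharge as the time point, which both measures share and which is the SAP's primary endpoint. Analyse the discharge value by a rank-based method adjusted for the baseline value and site, for example rank ANCOVA. Keep patients unable to walk as 0, and state that a gait record of 0 meters in 0 seconds counts as speed 0, since the ratio is otherwise undefined.
- **Estimate.** Report an effect measure that matches the rank test, such as the probability that an EMR patient does better than an SOC patient, with a confidence interval. Delete the reference to means.
- **Day 30/60/90 function.** Name the instrument, add its baseline score and site as covariates, and keep the BIC-based covariance choice.
- **Record.** The SAP is labelled final and already reports study data (22 SCID interviews, 14 diagnoses). Record the change as a dated amendment, and show the planned Mann-Whitney result alongside, stating which quantity it was run on.

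The cost is SAP wording, a short amendment and some code. No new data are needed.
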